4.5.4. Other Variables

Additional variables to be assessed include graft rejection or graft loss. These will not be entered as unsolicited adverse events but instead entered on the Graft Rejection or Loss eCRF.

Time to death variable will be assessed using the date of death located on the Death eCRF.

Time to withdrawal from the study because of intolerance or drug related adverse events will be assessed using the date treatment discontinued on the Study Status eCRF for all subjects that terminated early. Reasons for early termination will undergo a review, blinded to outcome value, to determine if the withdrawal was due to intolerance or a drug related adverse event.

Saliva is collected on Day 1 to determine H type 1 secretor status (phenotyping) and a buccal swab is also collected to perform FUT2 genotyping. Secretor status will be measured in the [name] Laboratory (CCHMC, Cincinnati, OH). Both phenotypic and genotypic evaluation will be performed to compare results of the two methods. Detection of secretor antigens (Le^b, Le^y, H types) and non-secretor antigens (Le^a and Le^x) will be performed using monoclonal antibodies by ELISA. In the case of discordant results, the results from the phenotypic method will be used to classify secretor status.

5. SAMPLE SIZE CONSIDERATIONS

Sample size calculations assume a 50% reduction in the median duration of diarrhea for the nitazoxanide-treated group compared to those receiving placebo. The median diarrhea duration for the placebo group is assumed to be 135 days, while the median diarrhea duration for the treatment group is assumed to be 67.5 days. Given these assumptions, a sample size of 64 subjects in each arm (128 total) is required to achieve 90% power using the Log-Rank test. Accounting for a 20% attrition rate, final sample size will be 80 in each arm (160 total).

Though discouraged, the protocol allows for subjects in either study group to receive additional nitazoxanide after 28 days. Under the assumptions of treatment efficacy, additional treatment received by placebo subjects would reduce the median duration of symptoms for the placebo group to be closer to that of the nitazoxanide-treated group. It is assumed that subjects who would have the worst study outcomes (longest time to clinical resolution of diarrhea) will be the most likely to receive additional treatment. Subjects receiving additional treatment will be imputed as having the worst outcome (time to resolution censored at 180 days). Accounting for this imputation method, the power attained for the primary comparison was computed via simulation (R version 3.0.3). Estimated power is displayed in [Table 2](#), varying the proportion of subjects in each study group who receive additional treatment.

For example, if 15% of placebo subjects receive nitazoxanide, and 5-10% of subjects in the nitazoxanide-treated group receive additional treatment, the power is estimated to be 91.2%. Note that implausible scenarios (where substantially more nitazoxanide subjects receive additional treatment than do placebo subjects) have been omitted from the table.

6. GENERAL STATISTICAL CONSIDERATIONS

6.1. General Principles

All continuous variables will be summarized using the following descriptive statistics: n (non-missing sample size), mean, standard deviation, median, minimum, and maximum. The frequency and percentages (based on the non-missing sample size) of observed levels will be reported for all categorical measures. In general, all data will be listed, sorted by site, treatment, and subject, and when appropriate, by visit number within subject. All summary tables will be structured with a column (or row) for each treatment group in the order from left to right (or top to bottom): Nitazoxanide 500 mg, Placebo. Where necessary, summary tables will be stratified with Nitazoxanide 500 mg presented in one table and Placebo presented in the table immediately following. Tables will be annotated with the total population size relevant to that table/treatment, including any missing observations.

6.2. Timing of Analyses

The study was stopped early due to low enrollment and other unforeseen challenges, and thus the primary CSR will be generated once the last subject last visit has occurred, data monitoring and cleaning is complete, and the database is locked. PK and microbiome endpoints will not be included and will instead be provided in addendums to the CSR.

6.3. Analysis Populations

A tabular listing of all subjects excluded from the analysis populations will be provided in the CSR ([Listing 5](#)).

6.3.1. Modified Intention-to-Treat (mITT) Population

The mITT population includes all randomized subjects who received at least one dose of assigned study drug. Analyses are performed according to randomized treatment assignment, not the treatment received. This analysis set will be used for all efficacy analyses and will be considered the primary analysis for the primary efficacy outcome measure.

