Diagnosis of Norovirus generally relies upon detection of Norovirus RNA or antigens in stool since cell culture is not available and direct visualization via electron microscopy is impractical.^(34, 51) Enzyme immunoassay (EIA) detection methods are also available commercially. Although simpler to perform, EIA assays have reduced sensitivity (58–93%) and specificity (85–100%) compared to RT-PCRs.^(36, 51) Qualitative or quantitative PCRs can be run on stool, vomitus, foods, and environmental specimens.⁽³⁴⁾ PCR methods generally use primers directed at highly conserved regions of ORFs 1, 2, and 3, including the POL region in ORF 1.^(20, 52) Sequencing the products of RT-PCRs allows tracking of individual strains, which may be useful in outbreaks.⁽¹⁴⁾ Several multiplex panels that detect Norovirus, among other common gastrointestinal pathogens, have recently become widely available.⁽³⁶⁾

The current mainstay of therapy for Norovirus is supportive.^(53, 54) Reduction of immunosuppression is commonly practiced since diarrhea is a common adverse effect of many immunosuppressive drugs, including mycophenolate mofetil. It remains unclear, however, if reduction of immunosuppression alone significantly improves clearance of Norovirus. There are

a few case reports that suggest that substitution of one of the immunosuppressive agents with one of the mTOR inhibitors may speed recovery, but the strength of this data is limited.^(6, 47) In these two cases, symptoms improved within days, and viral shedding was undetectable within weeks of changing to an mTOR inhibitor.

Table 2: Approved and Experimental Therapies with Norovirus Activity

Target	Compound	Assays/stage	Virus
Pol (nucl.)	2'-C-methylcytidine	Cell culture (infection)	MNV
		Cell culture (replicon)	NV
		Mouse infection	MNV
Pol (nucl.)	Ribavirin	Cell culture (replicon)	NV
		Cell culture (infection)	FCV
		Co-crystallization w/pol	NV
		Cell culture (infection)	MNV
Pol (nucl.)	2'-F-2'-methylcytidine	Cell culture (infection)	NV
Pol (nucl.)	B-D-N(4) hydroxycytidine	Cell culture (infection)	MNV
		Cell culture (replicon)	NV
Pol (nucl.)	2-Thio-uridine	Cell culture (infection), RdRp in vitro assay	FCV
Pol (nucl.)	6-Aza-uridine	Cell culture (infection), RdRp in vitro assay	FCV
Pol (nucl.)	Favipiravir (T-705)	Cell culture (infection)	MNV
Pol (nucl.)	2-thiouridine	Co-crystallization w/pol	NV
Pol (nucl.)	5-nitrocytidine	Co-crystallization w/pol	NV

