5.1 Subject Inclusion Criteria

Subjects should meet all of the following inclusion criteria

1. Male or female age ≥ 12 years.
2. Recipient of a solid organ or hematopoietic stem cell transplant.
3. Positive test result for Norovirus within 14 days of enrollment that is obtained as part of routine clinical care using a Norovirus testing available to the site.
4. Active GI symptoms (diarrhea or vomiting) that, in the opinion of the PI, are secondary to Norovirus.[#]
5. Willing and able to provide written informed consent and assent before initiation of any study procedures, consistent with local IRB policy.
6. Subjects must be of non-childbearing potential or if of childbearing potential, must be using an effective method of birth control or must be abstinent.
 - Non-childbearing potential is defined as surgically sterile or postmenopausal for $>$ one year.
 - Effective methods of birth control include the use of hormonal or barrier birth control such as implants, injectable contraceptives, combined oral contraceptives, intrauterine devices [IUDs] or condoms with spermicidal agents during study period. Female subjects must be using an effective method of birth control or practice abstinence and must agree to continue such precautions during the study and for 30 days after the Day 28 study visit.
 - A woman is eligible if she is monogamous with a vasectomized male. This subject is considered low risk and not required to use contraception.
7. Agrees to complete all screening requirements, study visits and procedures.

[#] Patients must have active diarrhea, which is defined as at least 3 days of Bristol 6 or 7 stools in the past 2 weeks prior to enrollment per patient report.

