7.1 Screening/Baseline/Treatment Phase

Any subject ≥ 12 years of age, recipient of a solid organ or hematopoietic stem cell transplant with a positive test for Norovirus within 7 days as part of routine clinical care will be approached to participate in the study. Once consent is obtained, then laboratory testing and medical history will be reviewed to determine eligibility unless local IRB waiver allows to review data prior to consent. Assessment required for eligibility may not be measured more than twice.

a. Screening/Enrollment/Baseline

- Consent/Assent will be reconfirmed with eligible subjects, consistent with local IRB policy for consent and assent of subjects.
- Subject and their chart will be reviewed to collect a medical history, concurrent medications.
- Urine pregnancy test will be obtained from women of childbearing potential. Results must be known and negative prior to dosing.
- WBC, TLC (Total Lymphocyte Count) Hb, Platelets (Derived from Complete Blood Count -within 3 days of enrollment).
- Creatinine, Alk Phos, AST, ALT, BUN, Bilirubin (Derived from Complete Metabolic Panel-within 3 days of enrollment).
- T Cell Subsets will be drawn unless CBC shows an ALC <100 .
- Samples to be sent to the central laboratory are collected and processed:
 - Buccal swab and saliva samples for secretor assay.
 - Stool for quantitative Norovirus RT-PCR and sequencing.
 - Stool for other pathogen testing.
 - Stool for Norovirus-specific IgA, IgG, and IgM studies.
- Serum for quantitative Norovirus-specific IgA, IgG, and IgM and total IgG.
- Randomization.
- Vital signs will be obtained (pulse, temperature, BP, respiration, height and weight).
- Weekly Recall Packet will be administered.
- Detailed Subject Reported Outcome and Severity Score Assessment.
- Physical examination will be performed.

- Plastic bag with two 30-count bottles of study product will be dispensed to the subject. The first dose of study product (nitazoxanide or placebo) will be given by the study team.

The study product (nitazoxanide or placebo) will be taken by the subject twice daily for 28 days.

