11 STATISTICAL CONSIDERATIONS

11.1 Study Hypotheses

A formal hypothesis test is planned to compare nitazoxanide to placebo with respect to the primary efficacy outcome measure. The time from randomization until clinical resolution of Norovirus for at least 48 hours through 180 days will be compared between the two study arms.

The null hypothesis is that there is no difference in time until clinical resolution between study arms, with a two-sided alternative. The test for primary efficacy hypothesis will be conducted using a Log-Rank test at the 5% two-sided level of significance.

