11.2 Sample Size Considerations

Sample size calculations assume a 50% reduction in the median duration of diarrhea for the nitazoxanide-treated group compared to those receiving placebo. The median diarrhea duration for the placebo group is assumed to be 135 days, while the median diarrhea duration for the treatment group is assumed to be 67.5 days. Given these assumptions, a sample size of 64 subjects in each arm (128 total) is required to achieve 90% power using the Log-Rank test. Accounting for a 20% attrition rate, final sample size will be 80 in each arm (160 total).

Though discouraged, the protocol allows for subjects in either study group to receive additional nitazoxanide after 28 days. Under the assumptions of treatment efficacy, additional treatment received by placebo subjects would reduce the median duration of symptoms for the placebo group to be closer to that of the nitazoxanide-treated group. It is assumed that subjects who would have the worst study outcomes (longest time to clinical resolution of diarrhea) will be the most likely to receive additional treatment. Subjects receiving additional treatment will be imputed as having the worst outcome (time to resolution censored at 180 days). Accounting for this imputation method, the power attained for the primary comparison was computed via simulation (R version 3.0.3). Estimated power is displayed in the following table, varying the proportion of subjects in each study group who receive additional treatment

		Proportion Receiving Additional Treatment in the Placebo Group						
		0%	5%	10%	15%	20%	25%	30%
Proportion re-treated in the nitazoxanide Group	0%	91.3%	91.6%	91.7%	91.6%	91.8%	92.0%	92.3%
	5%	91.4%	91.5%	91.6%	91.2%	91.2%	91.8%	92.5%
	10%	-	91.5%	92.0%	91.2%	91.8%	91.2%	92.2%
	15%	-	-	90.7%	90.7%	91.0%	91.6%	91.8%
	20%	-	-	-	87.3%	87.1%	87.0%	87.7%
	25%	-	-	-	-	74.0%	73.9%	75.2%
	30%	-	-	-	-	-	40.0%	40.9%

For example, if 15% of placebo subjects receive nitazoxanide, and 5-10% of subjects in the nitazoxanide-treated group receive additional treatment, the power is estimated to be 91.2%. Note that implausible scenarios (where substantially more nitazoxanide subjects receive additional treatment than do placebo subjects) have been omitted from the table.

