As Norovirus surveillance laboratories have observed that Norovirus type GII is predominant compared to Norovirus type GI and dual infection by both GI and GII viruses is rare, all specimens are tested for Norovirus GII viral load first ([name], [name], person communication). Only specimens that are negative for Norovirus GII viral load will be tested for Norovirus GI viral load. Subjects will only be analyzed for the viral load test type (Norovirus GII or Norovirus GI) that they tested positive for at baseline (Visit 01). If a subject initially tested positive for GI and later tested positive for Norovirus GII before they tested negative for Norovirus GI, the subject will be considered positive for Norovirus GI until they test negative for Norovirus GII and Norovirus GI. Subjects that did not test positive for either Norovirus GII or Norovirus GI at baseline will be excluded from the analyses. The first day of undetectable quantitative Norovirus PCR is the first day the subject had either a negative result or a result less than the lower limit of quantitation (LLOQ) for the viral load test type (Norovirus GII or Norovirus GI) that they initially tested positive for at baseline. Viral load will be quantified as the geometric mean of the replicates. Negative results will be imputed as $\frac{1}{2}$ the LLOQ and results greater than the upper limit of quantification (ULOQ) will be imputed as the ULOQ.

Initial Clinical Improvement in Norovirus Disease:

Initial clinical improvement in Norovirus disease through 28 and 180 days for at least 48 hours, is defined by:

- a. 50% reduction in number of episodes of vomiting and,
- b. Improvement in PO intake, as judged by the subjects and,
- c. 50% reduction in the number of episodes of diarrhea as classified by the subject by the Bristol Stool Chart as type 6 or 7 bowel movements.

The baseline values for number of episodes of vomiting and diarrhea will be the numbers provided on the first non-missing daily diary entry for the vomiting and diarrhea questions, respectively. Subjects must answer “yes” to the daily diary question “Did you eat your usual diet today?” to meet the improvement in PO intake criteria.

Detailed Patient-Reported Outcome (PRO) Measures:

Study personnel will administer detailed PRO questionnaires to subjects at Visit 01 (Day 1), Visit 05 (Day 28), Visit 08 (Day 60), Visit 10 (Day 120), and Visit 12 (Day 180).

Quality of Life.

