14.2.2 Efficacy/Immunogenicity Response Figures by Measure, Treatment, and Time Point

Figure 3: Kaplan-Meier Curves of Time to Initial Clinical Resolution by Treatment Group – mITT Population

[Implementation Note: Include (N=X) for each group in legend.]

[figure not shown]
Figures with similar format:

Figure 4: Kaplan-Meier Curves of Time to Initial Clinical Resolution by Treatment Group – Per Protocol Population

Figure 5: Kaplan-Meier Curves of Time to Initial Clinical Resolution by Treatment Group: Worst Case Scenario Sensitivity Analysis – mITT Population

Figure 6: Kaplan-Meier Curves of Time to Initial Clinical Resolution by Treatment Group and Duration of Symptoms – mITT Population

[Implementation Note: Y axis will be “Proportion Resolved”, x axis will be “Days Since Randomization”. Curves will include all subjects in the mITT Population that tested positive for GII at baseline. Include (N=X) for each group in legend. If subgroup has less than 5 subjects per treatment group, add footnote describing exclusion from figure.]

Figures with similar format:

[figure not shown]
Figure 7: Kaplan-Meier Curves of Time to Initial Clinical Resolution by Treatment Group and Duration of Symptoms – Per Protocol Population

Figure 8: Kaplan-Meier Curves of Time to Initial Clinical Resolution by Treatment Group and Duration of Symptoms: Worst Case Scenario Sensitivity Analysis – mITT Population

Figure 9: Kaplan-Meier Curves of Time to Initial Clinical Resolution by Treatment Group and Diary Compliance – mITT Population

Figure 10: Kaplan-Meier Curves of Time to First Negative Viral Load by Treatment Group – Norovirus GII, mITT Population

[Implementation Note: Y axis will be “Proportion Negative”, x axis will be “Days Since Randomization”. Curves will include all subjects in the mITT Population that tested positive for GII at baseline. Include (N=X) for each group in legend.]

Tables with similar format:

[figure not shown]
Figure 11: Kaplan-Meier Curves of Time to First Negative Viral Load by Treatment Group – Norovirus GII, Per Protocol Population

Figure 12: Kaplan-Meier Curves of Time to First Negative Viral Load by Treatment Group – Norovirus GI, mITT Population

Figure 13: Kaplan-Meier Curves of Time to First Negative Viral Load by Treatment Group – Norovirus GI, Per Protocol Population

Figure 14: Kaplan-Meier Curves of Time to First Negative Viral Load by Treatment Group and Duration of Symptoms – Norovirus GII, mITT Population

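### No supportive analysis of clinical resolution is planned in subjects positive by central PCR on Day 1, and the Figure 6 note wrongly limits the by-stratum resolution curves to GII-positive subjects

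*SAP*

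**What the plan says.** **Entry.** Protocol 5.1, repeated in SAP 4.3, sets this condition: "Positive test result for Norovirus within 14 days of enrollment that is obtained as part of routine clinical care using a Norovirus testing available". The test is whichever one the enrolling center has; no method is named or excluded. Protocol 7.1 describes the patients to be approached as those "with a positive test for Norovirus within 7 days as part of routine clinical care". On test accuracy, Protocol 2.1 says that "EIA assays have reduced sensitivity (58–93%) and specificity (85–100%) compared to RT-PCRs".

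**Analysis sets.** For mITT: "The mITT population includes all randomized subjects who received at least one dose of assigned study drug" (SAP 6.3.1). The per-protocol set (SAP 6.3.2) adds the eligibility criteria, whose only virologic element is the local test.

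**Central PCR.** Protocol 7.1 and Table 6 send a Day 1 stool from every subject for central quantitative RT-PCR. Under the Viral Load heading, SAP 3.3 states: "Subjects that did not test positive for either Norovirus GII or Norovirus GI at baseline will be excluded from the analyses". The denominators of Tables 21 to 28, 35 and 36 follow that rule.

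**Figure 6.** The title is time to initial clinical resolution by arm and symptom duration in the mITT population. The note says: "Curves will include all subjects in the mITT Population that tested positive for GII at baseline".

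**The concern.** Subjects whose diarrhea is not due to norovirus, or who have already cleared the virus, cannot show an antiviral benefit. They pull the hazard ratio for clinical resolution toward 1. The SAP foresees baseline PCR negatives and handles them for viral load, but gives the reader no view of the clinical endpoint without them. It also does not say whether the exclusion in SAP 3.3 stops at viral load, while SAP 6.3.1 says that mITT serves all efficacy analyses.

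The Figure 6 note is a plain inconsistency. Followed literally, it drops GI-positive and PCR-negative subjects from a clinical figure, so the figure would not match its table. With 31 subjects, losing a few could visibly change a curve.

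**Working it through.** **1. Planned re-analyses of the primary endpoint.** I looked in each for a restriction to Day 1 PCR positives.

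- Per-protocol population (SAP 8.1.1, Table 16): none.
- Worst-case censoring (8.1.1, Table 17): none.
- Excluding additional nitazoxanide, and excluding chromaturia (6.4, Table 18): none.
- Diary compliance (8.1.1, Table 19): none.
- Co-pathogen status (8.3, Table 34): none.
- Secretor status (11, Table 48): none.

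Table 7 lists ineligibility at baseline as a reason for mITT exclusion, which SAP 6.3.1 does not. That row would still rest on the local test.

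**2. The figure notes.** The same GII sentence stands under Figure 10, a GII viral-load figure, where it fits. It appears to have been carried over to Figure 6. Neither SAP 8.1 nor Table 16 has such a limit. Figures 7 to 9 are only said to share Figure 6's format, so they may inherit it. Figure 7 is titled per-protocol, so an mITT note cannot apply to it literally. The note to Figure 3 has no GII limit, and Figures 4 and 5 follow Figure 3.

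**3. The plan's own sample size.** Inputs from Protocol 11.1 and 11.2: 5% two-sided, medians 135 and 67.5 days, 64 per arm, 90% power. I assume exponential times and censoring at Day 180.

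- Event probability: 1 − exp(−ln 2 × 180/135) = 0.603 on placebo and 1 − exp(−ln 2 × 180/67.5) = 0.843 on nitazoxanide; mean 0.723.
- Events at 128 subjects: 128 × 0.723 = 92.5.
- Schoenfeld power: Φ(√92.5/2 × ln 2 − 1.96) = Φ(1.37) = 91.5%, against 91.3% in the plan's table.
- Lachin-Foulkes gives 65 per arm, against 64. The plan's figure reproduces.

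**4. How far an EIA entry test could mislead.** Positive predictive value = se × prev / [se × prev + (1 − sp)(1 − prev)]. Sensitivity of 58% and 93% and the 85–100% specificity range are from Protocol 2.1. So is the prevalence: 35% of solid organ recipients evaluated for diarrhea. The 95% row is an intermediate value inside the stated range.

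| Specificity | se 58% | se 93% |
|---|---|---|
| 85% | 0.203/0.3005 = 68% | 0.3255/0.423 = 77% |
| 95% | 0.203/0.2355 = 86% | 0.3255/0.358 = 91% |
| 100% | 100% | 100% |

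**5. Dilution of the hazard ratio.** A share f of subjects is infected, with hazard ratio 2.0. The rest have the placebo hazard in both arms. The active arm then has S(t) = f·exp(−ln 2·t/67.5) + (1 − f)·exp(−ln 2·t/135). The large-sample Cox estimate with censoring at Day 180 is:

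- f = 90%: 1.86
- f = 80%: 1.73
- f = 68%: 1.59

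Giving uninfected subjects a 75-day or 14-day median in both arms changes these by at most 0.03.

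**6. Power under the same assumption** (simulated log-rank, 10,000 runs). At 128 subjects, power is 92% with nobody uninfected, 84% with 10% uninfected and 74% with 20%. At 31 subjects without dropout it is 38%, 30% and 25%.

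**The case against.** - **The PCR result is used elsewhere and is displayed.** A reader might infer that nothing is analysed in Day 1 positives. That is not so: the time-to-negative and titer-change analyses are restricted to them. Table 20 gives Day 1 GII and GI positivity by arm. GI is tested only when GII is negative, so its GI row yields the Day 1 negatives, unless the fewer-than-five-per-arm rule removes it. Listing 17 shows every result. This stands, and it narrows the gap to the clinical endpoint.
- **The main display is sound.** A reader might infer that the primary curves describe a different population from the reported hazard ratio. Figure 3 carries no GII limit. Only the by-stratum display is affected for certain.
- **EIA use is inferred.** The entry wording permits it, but the documents do not say that any site used it, and Protocol 2.1 also calls multiplex panels widely available. Other filters apply: the investigator's attribution of symptoms, at least 3 days of Bristol type 6 or 7 stools, and exclusion of other identified infectious causes. The prolonged shedding described in Protocol 2.1 makes clearance before Day 1 less likely. This stands, and the dilution range includes zero.
- **A negative Day 1 PCR does not prove the wrong patient.** The central assay targets GI and GII (Protocol 8.2.2), while Protocol 2.1 lists GIV as a human pathogen too. A rectal swab may replace stool. This stands, and negative, missing and invalid results need to be reported apart.
- **At 31 subjects the added run cannot settle anything.** SAP 14.2 calls the analyses primarily descriptive, and power is about 38% before any dilution. This also stands.

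**Conclusion.** Two narrow points hold. No supportive analysis of clinical resolution is planned in subjects positive by central PCR on Day 1, and the Figure 6 note contradicts its own title, SAP 8.1 and Table 16. The second needs no assumption.

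The size of the first is illustrative: a hazard ratio of 1.86 to 1.59 in place of 2.0 if 90% to 68% of subjects are infected. The low end requires every subject to have entered on an EIA with 58% sensitivity and 85% specificity at 35% prevalence, and no other entry criterion to help. It also assumes exponential times and no effect in uninfected subjects.

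A reader might go further and conclude that mITT is the wrong primary set, or that a null result would be due to uninfected subjects. The documents do not support either. Analysing all treated, locally eligible subjects is legitimate, and a null result at this sample size is uninformative with or without the subset. Severity is minor.

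**What to change.** 1. Keep mITT as primary. Add to SAP 8.1.1 one supportive, descriptive repeat of the stratified Cox analysis in mITT subjects with a positive GI or GII central PCR on the Day 1 stool. Report Day 1 negative and missing or invalid results by arm.
2. State in SAP 3.3 that the exclusion of baseline PCR negatives applies only to the viral-load analyses.
3. Delete the baseline GII restriction from the Figure 6 note, and confirm that Figures 6 to 9 use the same subjects as Tables 16, 17 and 19.
4. Reconcile the 14-day window (Protocol 5.1, SAP 4.3) with the 7-day window (Protocol 7.1). With enrollment closed, this changes no analysis.

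The cost is wording, a shell correction and one model run on data already collected. The subset is defined at baseline, so it adds no post-randomization selection. Its drawback is a smaller n, and the existing fewer-than-five-per-arm rule may suppress some rows.
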